CFR	Code of Federal Regulations
CRF	Case Report Form
FDA	Food and Drug Administration
GCP	Good Clinical Practice
IRB	Institutional Review Board
EC	Ethics Committee
HCP	Healthcare Professional
CDC	US Center for Disease Control
SAE	Serious Adverse Event
AE	Adverse Event
ARDS	Acute Respiratory Distress Syndrome
UP	Unanticipated Problem

1. Background

1. Overview

During the continuing SARS-CoV-2 (COVID-19) pandemic, several studies have reported a significant difference in the rate of severe cases between adult females and adult males (42% vs 58%).¹ Among children under the age of 14, the rate of severe cases was reported to be extremely low.¹ To explain this difference, several theories have been proposed including cigarette smoking and lifestyle habits. However, no theory fits both the gender difference in severe cases as well as reduced risk in pre-pubescent children. Our past research on male androgenetic alopecia (AGA) has led us to investigate an association between androgens and COVID-19 pathogenesis.² In normal subjects, androgen expression demonstrates significant variation between men and women as well as between adults and pre-pubescent children.

SARS-CoV-2 primarily infects type II pneumocytes in the human lung. SARS-CoV-2 enters pneumocytes, by anchoring to the ACE2 cell surface receptor. Prior to receptor binding, viral spike proteins undergo proteolytic priming by the transmembrane protease, serine 2 (TMPRSS2).³⁻⁵ TMPRSS2 inhibition or knock down reduces ability of SARS-CoV-1 (a related virus to SARS-CoV-2) to infect cells in vitro.⁶ Additionally, TMPRSS2 also facilitates entry of influenza A and influenza B into primary human airway cells and type II pneumocytes.⁷

The human TMPRSS2 gene has a 15 bp androgen response element and in humans, androgens are the only known transcription promoters for the TMPRSS2 gene.⁸⁻¹⁰ In a study of androgen-stimulated prostate cancer cells (LNCaP), TMPRSS2 mRNA expression increase was mediated by the androgen receptor.¹⁰ Further, the ACE2 receptor, also critical for SARS-CoV-2 viral infectivity, is affected by male sex hormones with higher activity found in males.¹¹

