7.3 Subject Population(s) for Analysis

- The primary analysis will be based on the intent-to-treat (ITT) population. The data from all subjects enrolled in the study will be analyzed.
- The safety analysis will be based on a modified intent-to-treat (MITT) population i.e., subjects who received at least one dosage of the interventional treatment.
- Subgroup analysis based on: 1) age stratification; and 2) androgen status as defined by the “Gabrin sign” or “PCOS signs” will be conducted for the primary and secondary outcomes.

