Subgroup analysis based on: 1) age stratification; and 2) androgen status as defined by “Gabrín sign” or “PCOS signs” will be conducted for the primary and secondary outcomes.	Changed to include the subgroup analysis per 1) baseline score (severity of the disease), 2) gender and 3) hospital site. No hypothesis testing was performed in these subgroup analyses to avoid finding significant p-values by chance due to multiple comparisons. Androgen status was excluded from the subgroup analysis.	Several reasons led us to make these new subgroup analyses: 1. Age was lower than expected, lower age cut-offs did not show relevant findings to be reported, possibly in the future we may plan for a multivariate analysis with factors such as women post-menopause. Also, pre-determining age cut-offs for analyses were needed. Age

		
distribution graphs were included in the supplement.
 
2. Since the randomization scheme was changed in the small hospital located in the remote Amazon areas to control for sharing and unblinding in these regions (see randomization details in the supplement), we needed to evaluate if there was interaction between the overall effect size [recovery ratio, and all-cause mortality ratio] per city of sites. Important to say here that in the hospital centers located in the capital of the state of Amazonas, randomization scheme was performed as planned.3. Since men are by definition more androgenic it was important to evaluate the effects specifically.4. Finally, we checked if there were an interaction effect between the patients with more severe presentations such as baseline score 6 compared to 5, 4, 3.

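### The final plan drops both subgroup analyses pre-specified in section 7.3: age partly because of what the cut-offs showed, androgen status with no reason given

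*Combined protocol and SAP*

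**What the plan says.** Final protocol, section 7.3, commits to "Subgroup analysis based on: 1) age stratification; and 2) androgen status as defined by the" Gabrin sign or PCOS signs, and states that this "will be conducted for the primary and secondary outcomes".

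Final statistical plan, part 2 (Secondary Outcome Measures), subgroup row:

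- The analysis as done: "Changed to include the subgroup analysis per 1) baseline score (severity of the disease), 2) gender and 3) hospital site". No hypothesis tests are made in these subgroups; part 3 (General principles) provides 95% confidence intervals for them.
- Androgen status: "Androgen status was excluded from the subgroup analysis".
- Age: "Age was lower than expected, lower age cut-offs did not show relevant findings to be reported". The row mentions a possible future multivariate analysis, and adds: "Also, pre-determining age cut-offs for analyses were needed". What remains on age is that "distribution graphs were included in the supplement".

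The introduction and closing line of the final plan both place the changes in the period when the manuscript was being written.

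The Background (Overview) states the rationale: the team's earlier work on androgenetic alopecia "has led us to investigate an association between androgens and COVID-19 pathogenesis".

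**The concern.** A pre-specified subgroup analysis protects the reader because it is reported whatever it shows. If an analysis is run and then left out because its findings were not judged relevant, the reader sees a filtered set. Little variation of the effect with age would itself be a finding, and it is the kind of finding that this rule removes.

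Androgen status matters for a different reason. The trial is justified by an androgen mechanism, and androgen status was the planned modifier closest to that mechanism. Without it, the reader cannot see whether the effect differs between men with and without the Gabrin sign, or between women with and without PCOS signs.

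**Working it through.** No sample size, power or event figure enters this point, so the check is a comparison of texts.

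**1. Planned against done.** Section 7.3 lists two factors: age and androgen status. The final plan lists three: baseline score, gender and hospital site. None of the three is in 7.3, and neither 7.3 factor is in the final plan. So 2 of 2 planned factors are removed.

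**2. The reasons for age, one at a time.**
- *Age was lower than expected.* This may leave older strata sparse. It does not prevent estimates with confidence intervals.
- *Lower cut-offs showed nothing relevant.* This is a reason based on results. The plural indicates more than one cut-off; the number is not given.
- *Cut-offs should have been fixed in advance.* This is a good reason not to choose one now. It is not a reason to omit age, because age can be modelled as a continuous modifier without any cut-off.
- *Distribution graphs are supplied.* These show who was enrolled, not how the treatment effect varies with age.

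**3. The reasons for androgen status.** The rationale column has four numbered items. Item 1 deals with age, item 2 with site, item 3 with gender and item 4 with baseline severity. None explains why androgen status was excluded. By contrast, the same part of the plan gives an operational reason for each of the two secondary outcomes that it drops: inadequate reporting by sites for duration of new oxygen use, and lack of funds for the day 14 PCR test.

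**4. Whether gender replaces androgen status.** Item 3 justifies the gender subgroup on the ground that men are more androgenic. The protocol versions show that the planners did not treat the two as interchangeable:
- The male-only version, section 7.3, has age and androgen status by Gabrin sign.
- The final version adds a female cohort (3.2), randomizes within each cohort (3.3) and sizes each cohort at 294 (7.2). Its section 7.3 keeps androgen status and extends it with PCOS signs.

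Androgen status was therefore planned in addition to sex. A comparison of men with women cannot describe variation with androgen signs among men or among women.

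**5. Whether the data exist.** Age needs no new data, since the plan says that cut-offs were examined. For androgen signs this is unknown: sections 5.1, 5.2, 6.1 and 6.2 of the final protocol do not name Gabrin or PCOS signs among the items to be recorded.

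**The case against.** The strongest defence has four parts.

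- *The androgen rationale is still examined.* The gender subgroup was added on androgen grounds, and the Background opens with the difference in severity between men and women. This stands in part. A reader might infer that the trial no longer reports anything bearing on its rationale; the documents do not support that. What is lost is the narrower analysis by androgen sign.
- *The replacements were not picked for their results.* A reader might infer that all three were. The documents do not show this. Men and women were separate cohorts, randomized and sized separately, before results. Site was added because the randomization scheme changed at the small remote hospitals. Baseline score contrasts score 6 with lower scores, and section 4.1 had been widened from scores 3–5 to 3–6. Calling sex post hoc without qualification would mislead.
- *The change is disclosed.* This also stands. The row sets planned and done side by side and describes the replacements as new. Disclosure does not restore the missing estimates.
- *Fewer subgroups means less multiplicity.* This does not help. The plan already handles multiplicity by giving intervals without tests, and the same format suits age and androgen status.

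The change cannot be set aside as a mere log entry either: the column describing what was done is the current plan, and the defect lies in what it omits and why.

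**Conclusion.** The point holds in this form: both subgroup analyses of section 7.3 were removed at the manuscript stage, age in part because of its findings and androgen status without a stated reason, and gender is a coarse substitute for the latter.

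The size is 2 of 2 planned factors. That count describes reporting and does not measure bias. The primary conclusion does not depend on these subgroups, so this is a change that should be made rather than a flaw that undermines the trial.

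Two limits apply. First, the age finding rests on reading the plan's sentence as saying that cut-offs were run and their results seen; it is hard to read otherwise, but the cut-offs are not named. Second, the manuscript and its supplement are not among the documents, so only omission from the plan is established.

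A reader might also infer that androgen status was dropped because its result was unfavourable. Nothing in the documents shows that it was ever analysed, and the results-based reason is attached to age alone. The two omissions should be kept apart.

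**What to change.** In the subgroup row of the final statistical plan:

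1. Report the treatment effect by age, with 95% confidence intervals, for the primary and retained secondary outcomes whatever it shows. A continuous age modifier is preferable because it avoids a cut-off chosen after the fact. It is not literally the age stratification of 7.3, and the plan should say so. List every cut-off already examined.
2. Report estimates with 95% confidence intervals by Gabrin/PCOS status, with the number of subjects in whom status was recorded, or state why this cannot be done.
3. Label baseline score and site as added after the protocol. Describe sex as a pre-planned cohort and randomization factor that 7.3 did not list as a subgroup.

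The policy of no hypothesis tests in subgroups can stay. For age the cost is a few table or forest-plot rows from data already held, possibly with sparse strata if age is grouped. For androgen status the cost depends on what was collected; at the least it is one sentence of explanation.

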3.2 Study Design/Type

This study is designed as a prospective, interventional, placebo controlled, double-blinded, randomized parallel assignment study. The study will have 2 cohorts: men and women and 2 arms:

Arm 1: Subjects administered Proxalutamide 300mg q.d for 14 days + standard of care as determined by the PI at the site

Arm 2: Subjects administered Proxalutamide placebo 300mg q.d for 14 days + standard of care as determined by the PI at the site

Study Environment:

This is a multi-center study to be conducted at multiple hospitals (the sites). This exact protocol will be followed during the study. There will be one or more PIs. The study will be approved by the appropriate Ethics Committees (IRBs). Data collection will be performed at each site by study personnel under the supervision of the PI.

Study Design:

Phase I: Enrollment (within 5 days of admission to hospital):

1. Each subject will be evaluated for the inclusion and exclusion criteria

2. Each subject will undergo a physical examination
3. Each subject (or legally authorized representative) will complete and sign the Informed Consent Form
4. Each subject will be assigned a subject study number
5. Each subject will be randomly assigned to an Arm (Section 3.3)
6. Based on the Arm assignment, each subject will be administered the intervention
7. All information will be recorded in the appropriate CRFs

Phase II: Outcome Assessment at Site (days 1-28):

1. Each subject will be evaluated daily by the PI for the outcomes of this study
2. Based on the Arm assignment, each subject will be administered the intervention
3. The PI will assess each subject for any treatment related adverse events
4. All information will be recorded in the appropriate CRFs

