3.3 Randomization

During the enrollment phase (admission to hospital), each subject will be assigned a subject study number. The first subject will be assigned the number 001 and each subject thereafter will be assigned a consecutive number i.e., 002, 003, etc.

In each cohort, subjects will be randomized into 1 of 2 arms in a 1:1 ratio each receiving an interventional treatment.

Arm 1: Subjects administered Proxalutamide 300mg q.d for 14 days + standard of care as determined by the PI at the site

Arm 2: Subjects administered Proxalutamide placebo 300mg q.d for 14 days + standard of care as determined by the PI at the site

In each cohort, each subject will be randomized using an interactive web software: Randomizer.at. The blinding table layout will be a single block. The randomization method used will be permuted blocks of size 4.

This is a blinded study. Neither participants, nor investigators, nor the study team will be aware of treatment assignments prior to the final data base locks at the conclusion of the study (or the interim analysis).

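### Two randomisation schemes fed the trial, but the primary recovery comparison is a single unstratified chi-square with no named planned-scheme-only sensitivity analysis

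*Combined protocol and SAP*

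**What the plan says.** Protocol section 3.3 gives one scheme for all hospitals: "In each cohort, subjects will be randomized into 1 of 2 arms in a 1:1 ratio", and "The randomization method used will be permuted blocks of size 4". It makes no exception for remote hospitals, and section 3.2 adds "This exact protocol will be followed during the study".

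The Final Statistical Plan, section 2, reports a departure: "the randomization scheme was changed in the small hospital located in the remote Amazon areas to control for sharing and unblinding". For the specifics it says "see randomization details in the supplement". It then limits the departure: "in the hospital centers located in the capital of the state of Amazonas, randomization scheme was performed as planned". So two schemes contributed patients. The wording mentions a single small hospital but also refers to areas and regions in the plural, so the number of hospitals affected is unclear.

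The plan draws a consequence: "we needed to evaluate if there was interaction between the overall effect size [recovery ratio, and all-cause mortality ratio] per city of sites". It adds hospital site as a subgroup and promises 95% confidence intervals for subgroups (section 3), but "No hypothesis testing was performed in these subgroup analyses to avoid finding significant p-values by chance due to multiple comparisons".

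Sections 3 to 5 make the primary result the overall 14-day recovery ratio, by intention to treat, with a chi-square test. They name no stratum for sex cohort, site or scheme.

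**The concern.** A chi-square on the pooled two-by-two table treats all patients as if one mechanism had assigned them. If the remote hospital or hospitals used a different allocation ratio and also had a different recovery rate, site and treatment are confounded. The pooled ratio then moves away from 1 with no drug effect. If patients there were assigned in runs or as whole sites, they are not independent units and the chi-square standard error is too small.

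The plan gives the scheme change as the reason for looking at results by city, but the primary test takes no account of it. Nothing says how a difference between the capital and the remote sites would bear on the efficacy conclusion.

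**Working it through.** **Inputs from the documents.** 294 patients per sex cohort, so 2 × 294 = 588; placebo recovery 100 − 61 = 39%; target 39 + 14 = 53%, a ratio of 0.53/0.39 = 1.36, which reproduces the plan's figure; loss 3.5%; two-sided 5% level.

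**Assumptions, because the documents give no values.** Remote share f of 10, 25 or 50%; remote allocation 1:1, 2:1 or 3:1 in either direction; remote recovery 10 or 20 points above or below the capital's 39%; no drug effect.

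**Formula.** With n1, n0 patients per arm and expected recovery p1, p0, let d = p1 − p0. Let se0 be the chi-square's pooled standard error and se1 the standard error from the site-specific rates. Size = 1 − Φ((1.96·se0 − d)/se1) + Φ((−1.96·se0 − d)/se1).

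**One cell in full: f = 25%, 2:1 towards active, remote recovery 59%.**
- Remote: 147 patients, 98 active and 49 placebo. Capital: 441, or 220.5 per arm. Totals: 318.5 and 269.5.
- p1 = (98 × 0.59 + 220.5 × 0.39)/318.5 = 0.4515
- p0 = (49 × 0.59 + 220.5 × 0.39)/269.5 = 0.4264
- d = 0.0252; spurious ratio 1.06; se0 = 0.0411; se1 = 0.0405
- Size = 0.086 + 0.004 = 9.0%

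**All cells, by remote share (normal approximation).**

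| Remote share | Size, 1:1 | Size, 2:1 | Size, 3:1 | Centre of pooled ratio, 2:1 and 3:1 |
|---|---|---|---|---|
| 10% | 4.8-5.0% | 5.2-5.9% | 5.5-7.2% | 0.95-1.05 |
| 25% | 4.6-4.9% | 6.0-9.5% | 7.4-15.9% | 0.895-1.118 |
| 50% | 4.4-4.9% | 6.8-14.3% | 9.5-27.9% | 0.835-1.198 |

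Simulation at 20,000 trials per cell agrees. The 1:1 cells lie at 4.4-5.2%, and a CMH test by scheme stays at 4.7-5.3% throughout. When assignment really was 1:1, stratifying by sex and scheme costs no power: for 39% vs 53%, 88.7-93.1% against 87.7-93.1% for the chi-square.

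**Runs instead of individual assignment.** A rough design effect is f·[1 + (b − 1)ρ] + (1 − f), for run length b and intraclass correlation ρ. Size is then 2·[1 − Φ(1.96/√deff)]. For f of 20-50%, b of 4-20 and ρ of 0.01-0.10 (all assumed), deff runs from 1.006 to 1.95 and size from 5.1% to 16.0%. Nothing in the documents bounds b or ρ, and whole-site assignment could fall outside this range. Strata do not correct this.

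**What a capital-only analysis could show.** Patients per arm: n = 294 × (1 − f) × 0.965. Expected 95% interval around 1.36: exp{ln 1.36 ± 1.96·√[0.47/(0.53n) + 0.61/(0.39n)]}. The remote interval uses 294 × f × 0.965, taking 1:1.

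| Remote share | Capital n per arm | Power, 39% vs 53% | Capital interval | Remote interval |
|---|---|---|---|---|
| 10% | 255 | 89% | 1.12-1.65 | 0.76-2.42 |
| 25% | 213 | 83% | 1.10-1.68 | 0.94-1.96 |
| 50% | 142 | 66% | 1.05-1.76 | 1.05-1.76 |

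**The case against.** The strongest reply is that the harm rests on a supplement nobody here has read. It may describe the unit, ratio, dates and numbers in full. The only ratio in the final protocol is 1:1, nothing says it changed, and a wish to limit sharing and unblinding gives no reason for 2:1 or 3:1. This stands, so the sizes above are conditional.

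Second, the largest figures need half of all patients remote, 3:1 allocation and a 20-point gap. A small hospital fits the 10% row better, where size is at most 7.2%. This stands too.

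Third, the plan already looks at effects by city with 95% intervals, so the capital's row is close to a planned-scheme-only estimate. This largely stands. What is missing is its status as a sensitivity analysis of the primary result and a statement of what follows if it disagrees. The plan column also says hospital site, not city; on that reading the capital's centres must still be combined.

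A reader might go further and infer that the randomisation was compromised, or that the remote hospital used the consecutive runs of 20 in the superseded protocol version. The documents support neither. Nothing links that schedule, or the logged change of randomisation model of January 19, 2021, to the remote hospital. Nor are the details shown to be undocumented; they are only unseen here.

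**Conclusion.** The point holds as a gap in the primary analysis, not as a demonstration of bias. The plan states that two schemes were used and then tests the primary endpoint as if there had been one.

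If remote assignment was individual and 1:1, the chi-square is valid. Leaving out the sex strata then costs at most some precision and is not a validity error. If the ratio was unequal and recovery differed by site, the error rate rises to about 5-7%, 6-16% or 7-28% at remote shares of 10, 25 and 50%, under the assumed 2:1 to 3:1 ratios and 10-20 point gaps. If assignment was by run or site, a different analysis is needed. The documents do not show which case applies. Since an analysis that follows the actual assignment is nearly free, it should be reported.

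**What to change.** 1. Name the scheme used at the remote hospital or hospitals in the plan, taking it from the supplement: which hospitals, from when, unit of assignment, ratio and numbers by arm. Steps 2 and 3 depend on this.
2. If assignment was individual, report beside the plan's chi-square, labelled post hoc, a Mantel-Haenszel recovery ratio with 95% confidence interval and a CMH test stratified by sex cohort and scheme or site.
3. If assignment was by run, cluster or whole site, use instead a re-randomisation test that reproduces the actual scheme, or a cluster-aware analysis.
4. Combine the capital's centres into one estimate and name it the planned-scheme-only sensitivity analysis of the primary result. Show its own 95% interval beside the remote estimate. If the capital interval includes 1, or the two estimates diverge, say that the pooled conclusion leans on the changed-scheme sites.

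The cost is one paragraph and a few lines of code; sex and site are already used as subgroups. The downsides are real but small. It is one more post hoc analysis in a plan that was adjusted during manuscript writing, so both results must be shown. Intervals widen if the remote share is large, or if sites had a single arm, because such sites add nothing to a site-stratified test. A small remote share leaves the remote estimate imprecise.

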In December 2020, we completed a double-blinded, randomized, prospective, investigational study of Proxalutamide Treatment for Non-Hospitalized COVID-19 Male Patients (NCT04446429). The length of the study was 30 days. Proxalutamide was administered 200mg q.d. for 15 days. Men enrolled in the study were 50 years and older. Two hundred and sixty two men completed the study. 134 men were assigned to the Proxalutamide group and 128 men were assigned to the control group. Thirty five subjects were hospitalized in the control group compared to zero in the Proxalutamide group. The proportion of COVID-19 patients hospitalized was significantly different between the Proxalutamide and control arms; $\chi^2(1) = 42.051$, $p < .0001$. The difference in proportions was 27.30% with a 95%CI: [19.79%, 35.59%]. No subject receiving Proxalutamide died compared to 2 (1.56%) in the control group. There were no treatment related adverse event reported during the course of the study.

Based on the results of the Proxalutamide Treatment for Non-Hospitalized COVID-19 Male Patients study (NCT04446429), the purpose of this study is to assess the efficacy and safety of Proxalutamide as a treatment for hospitalized COVID-19 male and female patients.

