6.4.3 Reporting Unanticipated Problems to Subjects

Subjects will be informed of any UPs that occur as part of their participation in this trial.

7 Statistical Plan

7.1 *Statistical Methods*

I. General Principles:

- Double-blinded, placebo controlled randomized interventional study with a two-sided type I error rate of 0.05.
- Continuous variables will be expressed as median (interquartile range [IQR]) and categorical variables will be expressed as a number
- 95% confidence intervals will be calculated for the primary outcome
- Group comparisons will be analyzed by the Wilcoxon rank sum test or χ^2 test
- The placebo arm will be used as a reference group when calculating treatment effects
- Differences between rates of clinical improvement will be calculated using unadjusted ordinal logistic regression or Cox proportional hazard models
- Statistical analyses will be conducted using XLSTAT version 2020.5.1 (Addinsoft, Inc.)

II. Statistical Hypotheses:

The primary endpoint is the distribution of clinical assessments on the COVID-19 ordinal scale at day 14. The primary outcome will be analyzed using the Wilcoxon rank sum test.

The Null Hypothesis (H_0) is that the distribution of clinical assessments on the COVID-19 ordinal scale at day 14 among hospitalized COVID-19 subjects treated with Proxalutamide is equal to the distribution of clinical assessments on the COVID-19 ordinal scale at day 14 among hospitalized COVID-19 subjects treated with the Proxalutamide placebo

The Alternative Hypothesis (H_A) is that the distribution of clinical assessments on the COVID-19 ordinal scale at day 14 among hospitalized COVID-19 subjects treated with Proxalutamide is not equal to the distribution of clinical assessments on the COVID-19 ordinal scale at day 14 among hospitalized COVID-19 subjects treated with the Proxalutamide placebo

Mathematically written as:

$$H_0: P(X > Y) = P(Y > X)$$

$$H_A: P(X > Y) \neq P(Y > X)$$

Where X and Y are randomly selected clinical assessments from the two treatment arms in the study.

III. Primary Efficacy Analysis:

- The non-parametric Wilcoxon rank sum test (Mann Whitney U) will be used to assess the primary end point.
- P-values <0.05 will be considered significant. All statistical analysis will be based on the intent-to-treat (ITT) population. All missing data will be described.

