7.2 Sample Size Estimates

Assumptions:

- The sample size estimation is based on the results reported in the placebo arm of the Adaptive COVID-19 Treatment Trial (NCT04280705)
- On day 15, 61% of subjects in NCT04280705 placebo group remained hospitalized.
- The odds ratio of improvement in the ordinal scale in the Proxalutamide arm compared to the Proxalutamide placebo is at least 2.0
- The study has two arms with randomization at 1:1 ratio
- 90% power to detect an odds ratio of 2.0 using a two-tailed test with a type I error rate of 5%
- According to NCT04280705 protocol “The sample size to detect a given odds ratio for 1:1 randomization using a 2-tailed test at level α is estimated by the equation below. λ is the log odds ratio, p_i is the overall probability (combined over both arms) of being in the i th category of the K ordinal outcomes, and $z_{\alpha/2}$ and z_{β} are the $1 - \alpha/2$ and $1 - \beta$ quantiles of the standard normal distribution.”

$$\frac{12(z_{\alpha/2} + z_{\beta})^2}{\lambda^2(1 - \sum_{i=1}^K p_i^3)}$$

- The estimated distribution is based on NCT04280705 protocol scenario 4
- 3.5% of the subjects will not complete the study based on NCT04280705

Sample Size Estimate:

CONFIDENTIAL

This material is the property of the Applied Biology Inc. Do not disclose or use except as authorized.

Based on the assumptions above, we calculated that at a minimum we would need to recruit for each cohort 294 subjects (147 subjects in each arm) i.e., a total of approximately 600 subjects.

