--	--	-------------------------------------------------------------------------------------------------------------------------------------------------------------------------------------------------------------------------------------------------------------------------------------------------------------------------------------------------------------------------------------------------------------------------------------------------------------------------------------------------------------------------------------------------------------------------------------------------------------------------------------------------------------------------------------------------------------------------------------------------------------------------------------------------------------------------------------------------------------------------------------------------------------------------

3. General principles

As proposed in the final protocol	Done in the final statistical Plan	Rationale
Continuous variables will be expressed as median (interquartile range [IQR]) and categorical variables will be expressed as a number	Continuous variables were expressed as median (IQR) and categorical variables were expressed as a number and in a risk percentage.	Expression of the categorical variables only as a number is not sufficient to allow for calculation of risk ratios. Then, absolute risk ratios were calculated for primary (14-day Overall Recovery rate) and secondary outcomes (28-day recovery rate and 28-day all-cause mortality)
95% confidence intervals will be calculated for the primary outcome	95% confidence intervals will be calculated for the primary outcome, secondary outcomes and subgroup analysis.	All secondary outcomes expressed in ratios were reported along with the 95% confidence interval to allow for a better understanding of the effect sizes.
Group comparisons will be analyzed by the Wilcoxon rank sum test or χ^2 test	For all categorial effect sizes, hypothesis testing was performed with the χ^2 test, including risk ratios. 95% Confidence intervals were reported in results tables, for the primary endpoint Overall Recovery Ratio), along with the P value. For the Adverse AE table, P-values were included. Other outcomes described as median and IQR were compared with the Wilcoxon rank sum test.	The primary hypothesis testing previously stated was maintained. However, we explained in which cases the different tests were applied to increase transparency.

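### The AE table gets P-values as its only between-arm inference; without an interval, a non-significant row for an uncommon event does not show how much harm is left open

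*Combined protocol and SAP*

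**What the plan says.** The Background overview of the final protocol (the revision with male and female cohorts) says "the purpose of this study is to assess the efficacy and safety of Proxalutamide" in hospitalized patients of both sexes. Section 6.1 of that protocol describes the safety assessment as a summary of the incidence and type of adverse events. Section 6.3.7 captures Grade 3 and 4 events and SAEs to Day 28. Section 7.3 defines the safety population as everyone who received at least one dose.

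The final statistical plan, section 3, then sets out the reporting:

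- Display: "categorical variables were expressed as a number and in a risk percentage".
- Intervals: "95% confidence intervals will be calculated for the primary outcome, secondary outcomes and subgroup analysis". The stated reason is a better understanding of effect sizes.
- Tests: "For all categorial effect sizes, hypothesis testing was performed" with the chi-square test.
- Adverse events: "For the Adverse AE table, P-values were included".

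Risk ratios are named for 14-day recovery, 28-day recovery and 28-day mortality only. Death also gets a hazard ratio with its interval. On error rates, section 7.1 of the protocol states a "two-sided type I error rate of 0.05" under General Principles, and "P-values <0.05 will be considered significant" under Primary Efficacy Analysis.

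**The concern.** An AE row in this plan will carry n, % and a P-value. The P-value answers only whether the data are surprising if the drug adds no harm. For a safety purpose the useful question is how large an excess the data still allow, and the plan specifies nothing that answers it. For uncommon events in a trial sized for efficacy, most rows will be non-significant even if the drug doubles the risk. A reader of the results could then take a column of large P-values as reassurance that the data do not give, in a seriously ill population.

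The plan's own reasoning points the other way. In its subgroup row it drops hypothesis tests because multiple comparisons throw up significant P-values by chance, and it reports intervals instead. An AE table usually has many rows too, and it gets the reverse treatment.

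**Working it through.** **Inputs.** Two-sided alpha 0.05 (protocol 7.1). Allocation 1:1, with 294 per sex cohort, 147 per arm (protocol 7.2). Pooling both cohorts gives 2 × 147 = 294 per arm. Pooling is my reading: the plan makes sex a subgroup and does no testing within subgroups. The test is chi-square (final plan, section 3). AE rates are assumptions, because the documents give none for this trial.

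**The plan's own sample size.** The formula in 7.2 gives N = 12(1.960 + 1.282)² / [(ln 2)² (1 − Σp³)] = 262.4 / (1 − Σp³). The category probabilities are cited to another trial's scenario and are not printed, so 294 can be neither confirmed nor refuted. An assumed Σp³ of 0.05 to 0.15 gives 287 to 320 after dividing by 1 − 0.035, which brackets 294. The calculation concerns the efficacy scale only. No AE comparison is powered anywhere in the documents.

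**Power for a true doubling, 294 per arm.** All pairs of binomial counts were enumerated, and the probabilities of those with |z| > 1.96 were summed, where z = (p₁ − p₀) / √[p̄(1 − p̄) · 2/294], the uncorrected chi-square:

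| Placebo rate → drug rate | Power | Missed |
|---|---|---|
| 1% → 2% | 15% | 85% |
| 2% → 4% | 30% | 70% |
| 3% → 6% | 42% | 58% |
| 5% → 10% | 65% | 35% |
| 10% → 20% | 93% | 7% |

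With 300 per arm the first three become 16%, 30% and 43%. Fisher's exact test at 294 per arm would be lower: 9%, 22% and 35%. By the normal approximation, a doubling is missed more often than found when the placebo rate is below about 3.7%. Reaching 80% power would need about 2,319 per arm at 1% → 2% and 1,141 at 2% → 4%.

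**What an interval adds.** Take 18/294 (6.1%) on drug and 9/294 (3.1%) on placebo.

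- Chi-square: p̄ = 27/588 = 0.0459; SE = √(0.0459 × 0.9541 × 2/294) = 0.01726; z = 0.0306/0.01726 = 1.773; χ² = 3.14; p = 0.076.
- Newcombe interval: the Wilson limits are 3.91% to 9.47% (drug) and 1.62% to 5.71% (placebo).
  - Lower limit: 3.06 − √[(6.12 − 3.91)² + (5.71 − 3.06)²] = −0.4 points.
  - Upper limit: 3.06 + √[(9.47 − 6.12)² + (3.06 − 1.62)²] = +6.7 points.

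The row is non-significant, yet an excess of up to 6.7 points on a placebo rate of 3.1% is not ruled out. For a rarer event, 12/294 v 6/294 gives p = 0.15 and a risk difference of +2.0 points (−0.9 to +5.2); the risk ratio is 2.0 (0.76 to 5.26).

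**The case against.** Several stronger readings are tempting, and the documents do not support them.

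- **That harm is shown by P-values and nothing else.** The display rule in the same section puts counts and risk percentages beside them. A reader could see a doubling and work out an interval.
- **That p > 0.05 will pass for safety.** No section says so. The plan says only that P-values were included, protocol 6.1 is descriptive, and the sentence setting the 0.05 threshold sits under the primary efficacy analysis. The misreading is foreseeable, but it is not the plan's rule.
- **That safety rests on the AE table.** Protocol 3.6, 6.3.2 and 7.5 act on individual serious events, and death already gets intervals. These provisions stand, but none of them says how large an excess of non-fatal events the final data exclude.
- **That the test is weak for every event.** It is not: pooled, a doubling from 5% is found 65% of the time and from 10%, 93%.
- **That power within one sex is the relevant figure.** Power would be lower with 147 per arm, but no AE testing by sex is planned.
- **That the AE table of the earlier prostate cancer dose study (Study 4) shows how this trial will be read.** It is background from another trial and does not govern this plan.

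It is also true that low power comes from the sample size, and that an interval changes neither power nor significance. What an interval does is display what has not been excluded, and that argument survives.

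**Conclusion.** The point holds as a gap in reporting. P-values are the only between-arm inference specified for adverse events, while every other class of result, including death, has a 95% CI. For uncommon non-fatal events the chi-square test would miss a true doubling about 58% to 85% of the time, for placebo rates of 3% down to 1%, so a non-significant row would leave a large excess open without showing it.

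The size rests on assumed AE rates, on pooling the two cohorts, and on all randomized subjects being dosed; any undosed subjects lower the power slightly. The conclusion does not extend to common events. It is a cheap improvement worth making, and not evidence that the plan defines safety by non-significance.

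**What to change.** In section 3 of the final statistical plan:

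1. Add the AE table to the confidence-interval row.
2. In the group-comparison row, specify the risk difference (proxalutamide minus placebo) with a 95% CI by the Newcombe or Miettinen-Nurminen method, in the safety population of protocol 7.3. Report it for any SAE, any Grade 3-4 AE, discontinuation due to an AE, and each listed event.
3. State that p > 0.05 for an adverse event is not to be reported as absence of harm. The P-values may stay beside the intervals.

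The cost is a change of wording and one extra column from counts already tabulated, with no new data or patients. The downside is that some rows will visibly fail to exclude sizeable harm, so the safety statement will look less favourable.
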